### 6.4.4 Immunogenicity analysis

#### 6.4.4.1 General approach

For the statistical analysis of immunogenicity endpoints, data from enrolled participants will be used according to the initial randomization assignment regardless of how many injections they received. Additional analyses may be performed, limited to participants who received all scheduled injections per protocol. Assay results that are unreliable, from specimens collected outside of the visit window, or from HIV-infected participants postinfection are excluded. Since the exact date of HIV infection is unknown, any assay data from blood draws 4 weeks prior to an infected participant's last seronegative sample and thereafter may be excluded. If an HIV-infected participant does not have a seronegative sample postenrollment, then all data from that participant may be excluded from the analysis.

Discrete categorical assay endpoints (eg, response rates) will be analyzed by tabulating the frequency of positive response for each assay by antigen and treatment arm at each timepoint for which an assessment is performed. Crude response rates will be presented with their corresponding 95% CI estimates calculated using the score test method [70]. Fisher's exact tests will be used for the primary analysis comparing the IgG response rates of the arm with ALVAC primes followed by ALVAC + Bivalent Subtype C gp120 adjuvanted with MF59® boosts (Group 1) vs the aluminum hydroxide adjuvanted arm (Group 2) at Month 6.5 with a significant difference declared if the 2-sided p-value is  $\leq 0.05$ . Fisher's exact tests will also be used to compare IgA response rates between the arm with ALVAC primes and Bivalent Subtype C gp120 adjuvanted with MF59® boosts (Group 1) and the arm with ALVAC + Bivalent Subtype C gp120 adjuvanted with MF59® coadministered at all vaccination timepoints (Group 3) at Month 6.5; this is considered a separate primary objective and thus no multiplicity adjustment will be made. Fisher's exact tests will also be used to compare response rates between the unadjuvanted and adjuvanted arms at Month 6.5 and other time points; these analyses are viewed as secondary and therefore no multiplicity adjustment will be made.

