This approach will also be used to compare the arm with ALVAC primes followed by ALVAC + Bivalent Subtype C gp120 adjuvanted with MF59® boosts at Month 3, 6, 12 (Group 1) to the arm with ALVAC + Bivalent Subtype C gp120 adjuvanted with MF59® coadministered at all vaccination timepoints (Group 3).

Based upon previous AIDS Vaccine Evaluation Group (AVEG) and HVTN trials, missing 15% of immunogenicity results for a specific assay is common due to study

participants terminating from the study early, problems in shipping specimens, or low cell viability of processed PBMCs. To achieve unbiased statistical estimation and inferences with nonparametric tests and generalized linear models fit by generalized estimating equation (GEE) methods, missing data need to be missing completely at random (MCAR). MCAR assumes that the probability of an observation being missing does not depend upon the observed responses or upon any unobserved covariates but may depend upon covariates included in the model (eg, missing more among whites than nonwhites). When missing data are minimal (specifically if no more than 20% of participants are missing any values), then nonparametric tests and GEE methods will be used, because violations of the MCAR assumption will have little impact on the estimates and hypothesis tests. These models will include as covariates all available baseline predictors of the missing outcomes.

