If a substantial amount of immunogenicity data are missing (at least 1 value missing from more than 20% of participants), then using the methods that require the MCAR assumption may give misleading results. In this situation, analyses of the immunogenicity endpoints at a specific timepoint will be performed using parametric generalized linear models fit by maximum likelihood. These methods provide unbiased estimation and inferences under the parametric modeling assumptions and the assumption that the missing data are missing at random (MAR). MAR assumes that the probability of an observation being missing may depend upon the observed responses and upon observed covariates, but not upon any unobserved factors. Generalized linear models for response rates will use a binomial error distribution and for quantitative endpoints, a normal error distribution. For assessing repeated immunogenicity measurement, linear mixed effects models will be used. If the immunological outcomes are left- and/or right- censored, then the linear mixed effects models of Hughes [72] will be used, because they accommodate the censoring. In addition, secondary analyses of repeated immunogenicity measurements may be done using weighted GEE [73] methods, which are valid under MAR. All of the models described above will include as covariates all available baseline predictors of the missing outcomes.

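### Does the switch from Fisher's exact test to a binomial model above 20% missing data leave the primary response-rate comparison undefined?

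*Combined protocol and SAP*

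**What the plan says.** In Section 6.4.4.1, "Fisher's exact tests will be used for the primary analysis comparing the IgG response rates" of Group 1 and Group 2 at Month 6.5, with significance at a two-sided p-value of 0.05 or less. For the other primary contrast, Group 1 against Group 3, "Fisher's exact tests will also be used to compare IgA response rates". Neither sentence mentions missing data. Table 6-4 in Section 6.1.2 gives power for the same test with 30 evaluable participants per arm.

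Later in Section 6.4.4.1, missing data are introduced with the remark that "missing 15% of immunogenicity results for a specific assay is common". Two cases follow. When missingness is small, "specifically if no more than 20% of participants are missing any values", nonparametric tests and GEE methods are kept. When there is "at least 1 value missing from more than 20% of participants", methods that need data missing completely at random are judged potentially misleading, and "analyses of the immunogenicity endpoints at a specific timepoint will be performed using parametric generalized linear models fit by maximum likelihood". The form is given as follows: "Generalized linear models for response rates will use a binomial error distribution and for quantitative endpoints, a normal error distribution". On adjustment: "All of the models described above will include as covariates all available baseline predictors of the missing outcomes". No link, test statistic or fallback for an arm at 100% response is stated.

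**The concern.** Read separately, the two parts of Section 6.4.4.1 seem to give the same primary comparison two different tests. The second is only partly specified, and the choices left open can matter. HVTN 100 (Section 4.11.1) reports binding antibody in 100% of vaccinees on the MF59 regimen at Month 6.5. If one arm responds completely, the arm effect on a logit scale is infinite. A Wald test then cannot reject, while a likelihood-ratio test rejects too readily. Two analysts following the same text could reach different significance statements from the same IgG data.

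The 20% count adds to this. Its wording does not name an assay, visit or pair of arms, so a count across all visits is conceivable, and that would make the switch far more likely. The power in Table 6-4 would then describe a test that was not used.

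**Working it through.** **Inputs.** Arms of 36, 36, 36 and 24, total 132 (Table 3-1). Planned missing rate 15% at Month 6.5 (Section 6.1). About 30 evaluable per adjuvanted arm, since 36 × 0.85 = 30.6. MF59 response 100% (Section 4.11.1). RV144 rates of 92% and 94% (Section 6.1.2) stand in for alum as an assumption, because the documents give no alum rate for this protein.

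**The plan's own figure.** Enumerating all outcomes for a two-sided Fisher test at n = 30 gives power of 0.810 for 80% vs 42%, 0.808 for 90% vs 56% and 0.813 for 95% vs 64%. The 80% column of Table 6-4 therefore reproduces.

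**Chance of the switch, one assay at one visit.** The number missing is binomial.
- All 132: 20% is 26.4, so at least 27 must be missing. P = 5.6% at 15% missing.
- The 72 in one contrast: 20% is 14.4, so at least 15 must be missing. P = 11.4%.
- HVTN 100 gives a lower rate: 185 analysed (Table 4-8) of 210 recipients (Table 4-10), 1 − 185/210 = 11.9%, although that gap may include per-protocol exclusions. The chances fall to 0.3% and 2.1%.

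**What the choice of test does.** If at least 15 of 72 are missing, at most 57 remain, or about 28 per arm. Unadjusted p-values with the MF59 arm at 28/28:

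| Alum responders | Fisher | Likelihood ratio | Score |
|---|---|---|---|
| 22/28 | 0.023 | 0.003 | 0.010 |
| 24/28 | 0.112 | 0.016 | 0.038 |
| 25/28 | 0.236 | 0.038 | 0.075 |
| 26/28 | 0.491 | 0.092 | 0.150 |

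The logit Wald p-value is about 0.999 whenever one arm is at 100% and the other is not (checked at n = 30, standard error about 14,500). Type I error at n = 28, with both arms at 92% or both at 94%, is 8.7% at each rate for likelihood ratio, 4.6% and 3.3% for score, and 0.5% and 0.2% for Fisher. So a test of the same binomial model that holds its level does exist.

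**Chance that significance differs, given the switch.** With MF59 at 100% and n = 28:

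| True alum rate | Fisher vs likelihood ratio | Fisher vs score |
|---|---|---|
| 92% | 36.9% | 16.1% |
| 94% | 22.9% | 7.9% |
| 98% | 1.8% | 0.2% |
| 100% | 0% | 0% |

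**Combined**, for one antigen, assuming the switch and the responses are independent:
- 72 participants, 15% missing, alum 92%, likelihood ratio vs Fisher: 11.4% × 36.9% = 4.2%.
- The same, likelihood ratio vs logit Wald. Wald never rejects here, so Fisher's own power of 2.1% is added: 11.4% × (36.9% + 2.1%) = 4.4%.
- The same, score vs Fisher: 11.4% × 16.1% = 1.8%.
- 72 participants, 11.9% missing, alum 92%, likelihood ratio vs Fisher: 2.1% × 36.9% = 0.8%.
- 72 participants, 15% missing, alum 98%, likelihood ratio vs Fisher: 11.4% × 1.8% = 0.2%.

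**Count across visits.** Suppose 15% are missing at each of Months 6.5, 12, 12.5 and 18, with a share d lost at all four and the rest sporadic at rate s, where d + (1 − d)s = 0.15. The share with any value missing is d + (1 − d)(1 − (1 − s)^4). For d = 0.10 this is 28.4%, and the switch among 132 has a chance above 98%. For d = 0.13 it is 20.7% and 57%. For d = 0.15 it is 15% and 5.6%. The documents do not give this split.

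**The case for a change.** The strongest argument for a change is that this is a primary test and a few words would settle it. Reading the model as the replacement for Fisher decides only which method applies. Its link and statistic would still be unnamed, and at 28/28 vs 24/28 the likelihood-ratio and score tests fall below 0.05 while Fisher and Wald do not. Complete response on MF59 has been observed, not merely imagined. The words of the 20% rule do not exclude a count over visits, and that reading could make the switch almost certain.

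Much of this is correct: the omissions are real, and the p-values do differ. Three things limit it. First, the context of the rule favours one assay at one visit: the 15% refers to a specific assay, Section 6.1 ties it to Month 6.5, and the plan treats analyses at one timepoint separately from repeated measurements, which go to mixed models. The high switch probabilities need the less natural reading and an assumed dropout pattern. Second, the differences concern significance, not direction, and much of the gap from Fisher reflects its conservatism near 100%. Third, keeping Fisher on complete cases above 20% missing would set aside the plan's stated reason for switching. That is a trade-off, not a correction.

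**Conclusion.** The concern does not call for a change. Section 6.4.4.1 is a two-branch rule: Fisher's exact test applies up to 20% missing, and the likelihood model replaces it above that. The omissions (link, test statistic, handling of a 100% arm, explicit base of the count) are details of a contingency. An analyst who saw a complete-response arm would notice that the Wald result is unusable and choose a score-based, exact or penalised test. The score method is already used for the response-rate intervals in the same section.

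For an assay-and-visit count at 15% missing, the switch has a chance of about 6% to 11%. The choice of test then alters IgG significance in about 4% of trials for one antigen, with MF59 at 100%, alum at 92% and the likelihood-ratio test chosen. The figure falls to 1.8% with the score test, 0.8% at 11.9% missing and 0.2% with alum at 98%, and to zero if both arms reach 100%. A lower alum rate could raise the 4%, but on this count the total cannot exceed the chance of the switch itself.

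Little would be gained in any case. At 100% vs 92% or 94% with n = 30, Fisher has power of only 2.9% or 0.8%. The primary endpoint is occurrence and level, so level does most of the work there, and its normal model is not affected by complete response. The documents show no comparable ceiling for IgA.

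### Above 20% missing data, the single-timepoint GLM is a complete-case regression and is not unbiased under the plan's own definition of MAR

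*Combined protocol and SAP*

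**What the plan says.** Section 6.4.4.1 of the combined protocol and SAP sets two branches.

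- **No more than 20% of participants missing any value:** "then nonparametric tests and GEE methods will be used, because violations of the MCAR assumption will have little impact" on results. The plan says these methods need MCAR, meaning that the chance of a missing value "does not depend upon the observed responses or upon any unobserved covariates but may depend upon covariates included in the model". On covariates: "These models will include as covariates all available baseline predictors of the missing outcomes".
- **Above 20%** ("at least 1 value missing from more than 20% of participants"): the plan warns that MCAR methods may mislead, and "analyses of the immunogenicity endpoints at a specific timepoint will be performed using parametric generalized linear models fit by maximum likelihood", with a binomial error for response rates and a normal error for levels. The definition is now wider: "MAR assumes that the probability of an observation being missing may depend upon the observed responses and upon observed covariates". The claim at issue is "These methods provide unbiased estimation and inferences under the parametric modeling assumptions and the assumption that the missing data are missing at random (MAR". The covariate rule is the same: "All of the models described above will include as covariates all available baseline predictors of the missing outcomes".

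In the second branch, linear mixed models are assigned to repeated measurements, with a censored-data version if needed. Weighted GEE is an optional secondary analysis. Neither is assigned to the Month 6.5 arm comparison. Both primary immunogenicity endpoints are at that single timepoint (Section 5.1). The named tests for them are Fisher's exact for response rates, and Wilcoxon, t-test or Lachenbruch's test for levels.

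**The concern.** By the plan's own definitions, MAR differs from MCAR in one respect: missingness may also depend on observed responses. The switch to a likelihood method is meant to cover that case. A likelihood can do so only if those responses are in it, and a model for one timepoint holds one outcome and baseline covariates. The plan would then report a complete-case result as MAR-valid just when it judges missingness serious enough to change method.

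At stake are the Month 6.5 comparisons of Group 1 with Group 2 (IgG) and of Group 1 with Group 3 (IgA). If participants with weaker earlier responses are lost more often in one arm, the contrast shifts and the planned fallback does not correct it.

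**Working it through.** **The plan's own figures.** The missing-data text gives no result to reproduce. The nearest figures are the evaluable numbers in Section 6.1.2. With 15% missing, 36 × 0.85 = 30.6 and 24 × 0.85 = 20.4, matching the stated 30 and 20. Fisher power at 30 per arm also reproduces: 80% against 42% gives 0.810, and 80% against 37% gives 0.902.

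**Step 1: what the fallback uses.** Let R = 1 if the Month 6.5 outcome y is observed, with arm and baseline covariates x.

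- GLM likelihood: the product of f(y | arm, x) over participants with R = 1. Those with R = 0 contribute nothing.
- GLM score equation: Σ R · D′V⁻¹(y − μ) = 0, where D is the derivative of μ with respect to the coefficients.
- GEE at the same timepoint has clusters of size one, so its equation is identical.

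Fitted to the same data, the two sets of estimates agreed to about 1e-15, for normal and for binomial outcomes. The fit is unbiased only if R is unrelated to y given arm and x, which is the plan's MCAR condition.

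**Step 2: what it removes and what it leaves.** Simulation with true difference 0, outcome SD about 1, about 23% missing, missingness driven in one arm only, and an assumed correlation of 0.5 between covariate and outcome. Entries are bias in the arm difference, large samples.

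| Missingness depends on | Unadjusted | GEE + covariate | GLM + covariate | Joint likelihood with earlier response |
|---|---|---|---|---|
| Baseline covariate | -0.147 | -0.002 | -0.002 | 0.000 |
| Earlier response | -0.182 | -0.113 | -0.113 | 0.002 |

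For response rates with covariate-driven loss, the bias falls from -3.8 to -0.1 percentage points.

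**Step 3: size on the plan's scale.** Assumptions: SD = √2.06 = 1.435 (the variance in Section 6.1.2, read as natural log); correlation ρ between the earlier and Month 6.5 responses; random loss in one arm; in the other, odds of loss multiplied by OR per SD lower earlier response; no covariates. Then bias = ρ × 1.435 × m, where m is the mean standardised earlier response among those retained, by numerical integration of the logistic loss model.

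| Loss | OR | m | Bias, ρ = 0.6 | Bias, ρ = 0.8 |
|---|---|---|---|---|
| 25% | 2 | 0.159 | 0.14 | 0.18 |
| 25% | 3 | 0.228 | 0.20 | 0.26 |
| 33% | 2 | 0.208 | 0.18 | 0.24 |
| 33% | 3 | 0.295 | 0.25 | 0.34 |

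As false geometric mean ratios, the extremes are exp(0.14) = 1.15 and exp(0.34) = 1.40. Simulation at 36 per arm, with 10% random loss in the other arm, agrees. Type I error was about 6-14% against a nominal 5%. A joint likelihood using the earlier response had bias near zero and about the same or slightly smaller spread.

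**Step 4: how often the branch applies.** More than 20% of 132 means 27 or more participants. With 15% missing independently at one visit, the binomial probability is about 6%. The trigger counts any missing value. If two visits were each 15% missing independently, 1 − 0.85² = 27.75% would lack a value and the probability is about 98%. Dropout makes losses overlap, which lowers the second figure.

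**Step 5: which other responses exist.** Footnote 6 of Appendices F to I starts with M0 (binding antibody), M6.5 and M12. M0 is pre-vaccination and should say little about response. M12 is absent for anyone who left before Month 6.5, so for that loss a joint model on these three visits leaves the bias unchanged.

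**The case against.** **The fallback is not empty.** A reader might infer that it removes no bias and needs the same assumption as everything it replaces. The documents do not support that. Fisher's exact, Wilcoxon, t- and Lachenbruch tests carry no covariates, while the fallback must include all available baseline predictors of the missing outcomes. Step 2 shows that it removes nearly all bias from such predictors, and part of it when an earlier response drives loss. The equivalence holds against covariate-adjusted GEE only.

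**Unequal loss alone is harmless.** A reader might also infer that different loss in open-label Group 3 and blinded Group 1 would pass straight into that contrast. It would not: loss that differs only by arm causes no bias. It must also depend on response, and no document shows that it does.

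**The sizes are weakly grounded.** The correlations and loss odds are assumed. The 2.06 is an RV144 IgG variance among responders with no log base stated, whereas Group 1 against Group 3 is the IgA comparison. No covariates were simulated. The scenarios also do not reach the trigger through Month 6.5 alone: with 10-15% loss in the other two arms, total loss is 14-16% of 132 (25% case) or 16-19% (33% case). Missing values at other visits would have to supply the rest. All of this stands, and makes the sizes illustrative.

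**Better methods are already listed.** True, but for repeated measurements or as optional secondary work. Without an earlier assayed response they would not help with dropout before Month 6.5, and missingness driven by an unassayed response is not MAR as the plan defines it. That limit shapes the fix.

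**Conclusion.** The point holds in a limited form. The unqualified MAR statement is wrong for the single-timepoint GLM, because that model cannot account for missingness that depends on responses at other visits. Its estimates are those of a GEE with the same covariates, and its advantage over the unadjusted tests is confined to included baseline covariates. This conclusion is algebraic and rests on no assumed input.

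The bias of about 0.14-0.34 ln units depends on the assumptions in Step 3 and is not a forecast. Whether the branch is reached depends on how losses overlap across visits. The plan should be corrected before unblinding, but nothing here shows that the Month 6.5 results will be biased.

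**What to change.** 1. In Section 6.4.4.1, restrict the MAR statement for the single-timepoint GLM to missingness that depends on covariates in the model.
2. In the branch above 20%, report the Month 6.5 arm contrast from methods the plan already names, using all assayed visits: for levels, the linear mixed model (the censored-data version where applicable); for response rates, weighted GEE, with weights built from responses at other visits and baseline covariates.
3. M0 and M12 help only with intermittent losses, such as shipping failures. Where loss is mainly dropout before Month 6.5, add the earlier post-vaccination binding-antibody result: M3.5 in Groups 1, 2 and 4, and M1.5 in Group 3. Assay it in everyone with a sample, not only in those missing Month 6.5, because the model needs participants with both values. Run the isotype of each primary: IgG for Group 1 against Group 2, IgA for Group 1 against Group 3.

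Cost: revised SAP wording, modest programming and some extra assay runs. The serum is already scheduled for collection in Appendices F to I, and Section 10.3 allows assays at other timepoints depending on the responders observed. No new visit or blood draw is needed.

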#### 6.4.4.2 Analysis of CD4+ T-cell response as measured by the ICS assay

The analysis of the CD4+ T-cell response rate as measured by the ICS assay will be evaluated and compared as described under the general approach. The positivity call for each peptide pool will include a multiple comparison adjustment for the number of peptide pools used in the assay using the discrete Bonferroni adjustment. The magnitude of response will be analyzed as described for quantitative data in the general approach section. Graphs will be used to display the background-subtracted magnitudes for each participant by protein, treatment arm and timepoint, with a box plot of data from positive responders superimposed on the individual data values. Statistical testing comparing the magnitudes will be based on positive responders only. The same approach will be used to analyze other T cell subsets of interest.

